5.6 Schedule of assessment

Visit 1 Screening and informed consent. Outcome questionnaires at baseline.

- Visit 2 Diagnostic test.
- Visit 3 FJIs or sham procedure.
- Visit 4 Outcome questionnaires at 6 weeks.
- Visit 5 Outcome questionnaires at 3 months.
- Visit 6 Outcome questionnaires at 6 months.

There will be 6 study visits in total -3 visits are part of routine clinical practice (patients are seen in the pain clinic, referred for FJIs, then followed-up at 6 to 8 weeks), and 3 visits are additional. We anticipate that it will take up to one hour to complete the set of outcome questionnaires. The outcome questionnaire visits will take place in a research nurse-led clinics.

5.7 Follow-up procedures

Participants will be complete the study 6 months following their active or sham treatment. The patients would be followed up by the pain clinics as per routine NHS practice after completion of study.

5.8 Study evaluations

Assessment tools/notes

- Pain intensity and characteristics Brief Pain Inventory (BPI) (Short Form) Modified, with its 11-point NRS Short Form McGill Pain Questionnaire
- 2. Use of co-analgesics in the previous week
- 3. Early withdrawal from the study for lack of efficacy in pain relief, or for side effects
- 4. Expectation of benefit (asked at baseline only) 0 to 6 scale, ranging from "expect no improvement" to

"expect total improvement"

- 5. Health-related quality of life EQ5D-L, 12-item Short Form Survey (SF-12)
- 6. Functional impairment: Oswestry Low Back Pain Disability Questionnaire, Pain Self Efficacy Questionnaire (PSEQ)
- 7. Satisfaction with treatment (after treatment given)
- 8. Complications and adverse events: These will be the subjects of enquiry at visits and following procedures, as well as through spontaneous reporting at any time. They will be acted upon as necessary, and for the patient's benefit, and fully documented in the clinical research form and the hospital notes for later analysis.
- Co-Psychological well-being: Hospital Anxiety and Depression Scale, Pain Catastrophizing Scale, SF-12, BPI
- 10. Healthcare utilisation and costs, and impact on productivity: Published national costs to calculate costs of delivering each treatment arm/intervention and downstream healthcare utilization, Stanford Presenteeism Scale 6 Self-reported measures of sickness absence over the previous 3 months. Text message/telephone follow-up to assess healthcare utilisation. This is to ensure comprehension and up-to-date data collection

5.9 Laboratory assessments

Laboratory assessments are not required in this study.

5.10 End of study definition

The study will be completed when all randomised patients have completed the final follow-up assessments.

5.11 Procedures for unblinding

Unblinding can only be undertaken by an authorised person who is documented on the site delegation log. In the event of an emergency, the investigator will decide the necessity of unblinding the subject's treatment assignment. The blinded treatment assignments will be accessible to the investigator should a subject need to be unblinded in an emergency using the unblinding envelopes. If unblinding occurs, the investigator must record the reason for unblinding, as well as the date and time of the event. Corresponding information will be recorded on the CRF by the investigator.

5.12 Subject withdrawal

Each participant has the right to withdraw study at any time. In addition, the investigator may discontinue a participant from the study at any time if the investigator considers it necessary for any reason including:

- Pregnancy
- Ineligibility (either arising during the study or retrospective having been overlooked at screening)
- Significant protocol deviation
- Significant non-compliance with treatment regimen or study requirements
- An adverse event which requires discontinuation of the study medication or results in inability to continue to comply with study procedures
- Disease progression which requires discontinuation of the study medication or results in inability to continue to comply with study procedures
- Consent withdrawn from treatment but continue in the study
- Consent withdrawn from study
- Lost to follow up

The reason for withdrawal will be recorded in the CRF.

5.13 Data collection and follow up for withdrawn subjects

The patients and all identifiable data collected will be withdrawn from the study and excluded in the analysis. Data that is not identifiable by the research team will be retained.

6. Laboratories

This section is not applicable to the study.

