8.5 Statistical analysis

As this is a feasibility study, we do not propose to formally inferentially test differences in outcomes or costs between or within the groups. Recruitment and attrition rates will be calculated with 95% confidence intervals. We shall report mean and standard deviations for primary and secondary outcomes for the two groups at baseline and all follow-up visits.

9. Data Handling & Record Keeping

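### Section 5.13 excludes withdrawn patients from the analysis, which conflicts with the study's aims of measuring attrition and outcome SD and may bias both estimates

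*Protocol*

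**What the plan says.** Section 5.13 of the protocol states: "The patients and all identifiable data collected will be withdrawn from the study and excluded in the analysis". A second sentence makes an exception for anything that the team cannot trace to a person, which is kept.

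Section 5.12 determines who is affected. A participant may withdraw at any time, and the investigator may discontinue a participant for any reason thought necessary. The listed reasons include:

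- "An adverse event which requires discontinuation of the study medication or results in inability to continue to comply with study procedures"
- "Significant protocol deviation", and likewise significant non-compliance
- "Lost to follow up"
- "Consent withdrawn from treatment but continue in the study"

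The list also covers pregnancy, ineligibility, disease progression and withdrawal of consent from the study. The reason is recorded in the CRF.

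Other sections make these patients part of what is measured:

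- **Section 2.2:** objective 1 is recruitment and retention, objective 1a includes protocol violations and adverse outcomes, and objective 4 is the outcome SD for the definitive trial.
- **Section 5.8, item 3:** one study evaluation is "Early withdrawal from the study for lack of efficacy in pain relief, or for side effects".
- **Section 8.1:** a CONSORT flow gives the numbers randomised and the numbers with completed outcomes.
- **Section 8.5:** "Recruitment and attrition rates will be calculated with 95% confidence intervals".

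**The concern.** A feasibility study has few products, and two of the main ones here are the attrition rate and the outcome SD. The exclusion rule acts on exactly the patients who define attrition. It also removes some of those who carry the protocol violations and adverse outcomes that objective 1a sets out to analyse.

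The rule is not confined to patients who ask for their data to be erased. Read literally, it covers someone lost after the 3-month visit, whose baseline, 6-week and 3-month scores are perfectly usable. It also covers someone who stops treatment and remains in the study. That entry contradicts itself, because a patient cannot both continue in the study and be withdrawn from it.

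If attrition were understated, retention could look adequate for a definitive trial when it is not. If the SD were understated, the definitive trial would be planned too small.

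**Working it through.** **Inputs.** Section 8.2 gives 60 randomised 1:1, 20% assumed attrition, a second figure of at most 1 in 3 dropping out, and planning values for the main trial: a 2-point difference on the pain NRS, SD 3.0 to 4.0, 90% power and 5% alpha. The sidedness of alpha is not stated, so two-sided is assumed. The protocol does not say how withdrawn and retained patients differ in pain. The mean gaps below are assumptions.

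**Plan's own figure.** 60 × (1 − 0.20) / 2 = 24 complete data sets per arm, which agrees with section 8.2.

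**Attrition.** With all randomised patients kept:

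- 12/60 = 20% (exact 95% CI 10.8% to 32.3%)
- at the 1-in-3 maximum, 20/60 = 33.3% (21.7% to 46.7%)

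Suppose that k of the L non-completers are recorded as withdrawn and leave both numerator and denominator. Reported attrition is then (L − k)/(60 − k):

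| True losses L | Excluded k | Reported |
|---|---|---|
| 12 | 3 | 9/57 = 15.8% |
| 12 | 6 | 6/54 = 11.1% |
| 12 | 12 | 0/48 = 0% |
| 20 | 10 | 10/50 = 20.0% |
| 20 | 12 | 8/48 = 16.7% |

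The last two rows show true attrition at the protocol's maximum being reported at or below its 20% planning value. The protocol does not say that attrition will be computed this way. The table shows what the literal rule permits.

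**Outcome SD.** Let w be the share withdrawn, d the mean gap in pain score between withdrawn and retained patients, and assume the same SD within both groups. The retained patients' SD is then √(SD² − w(1 − w)d²). With w = 0.20, w(1 − w) = 0.16. Main-trial size uses the normal approximation, n per arm = 2(1.960 + 1.282)² SD² / 2², rounded up and doubled:

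| Assumed gap d | True SD 3.0: estimated SD (total N) | True SD 4.0: estimated SD (total N) |
|---|---|---|
| 0 | 3.00 (96) | 4.00 (170) |
| 1 | 2.97 (94) | 3.98 (168) |
| 2 | √(9 − 0.64) = 2.89 (88) | 3.92 (162) |
| 3 | √(9 − 1.44) = 2.75 (80) | 3.82 (154) |

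Section 8.2 gives totals of 100 to 160. The 96 and 170 are this formula's values at the same SDs and serve only as the reference for the comparison.

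For scale, 48 patients in two arms (46 degrees of freedom) give a 95% CI for an SD that runs from 0.83 to 1.26 times the estimate. The possible bias is smaller than the sampling error. Unlike sampling error, it is avoidable.

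**Does the retention sentence rescue the rule?** Section 9.1 says that no identifiable information is collected. The same section requires a screening log with initials and a unique number, and uses initials and date of birth when data go to third parties. Section 9.2 lists a patient identification log. On the first statement 5.13 removes almost nothing, and on the others it removes nearly everything. The text does not decide between them.

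**The case against.** The strongest reply is that the rest of the protocol preserves what 5.13 appears to remove, and much of that stands.

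- **Attrition.** The CONSORT flow in 8.1 reports randomised and completed numbers, and 5.12 puts each withdrawal reason in the CRF. Randomised minus completed still gives 12/60. A reader might infer that the attrition rate is bound to be wrong, or that differences in withdrawal between arms are hidden. The documents do not support that. They contain conflicting instructions, one of which yields the right number.
- **SD.** A reader might infer that the poor-outcome tail is cut off. Nothing in the protocol says that withdrawn patients have worse pain, and pregnancy, overlooked ineligibility or loss to follow-up need not track pain. Patients truly lost have no later scores under any rule, so 5.13 affects only data that exist.
- **Adverse events.** It is tempting to say that these data are lost. They are not. Sections 5.8 (item 8), 7.3 and 7.4 require them to be documented, and 7.6 requires an annual risk-benefit analysis of all events. Only their place in the final analysis is unclear.
- **Breadth of 5.12.** Investigator discontinuation is discretionary, deviations and non-compliance must be significant, and an adverse event counts only if it stops study medication or prevents study procedures.

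These points limit the certainty and the size of the harm, but they do not make the sections compatible. Nor is this a detail left to a later analysis plan: the protocol itself fixes the rule, and an analysis plan that kept these patients would contradict it.

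**Conclusion.** The point holds as a conflict that may bias the feasibility estimates. Sections 5.12 and 5.13 cannot be followed literally together with objectives 1, 1a and 4, section 5.8 item 3, the CONSORT flow in 8.1 and the attrition rate in 8.5. Applied as written, the rule also discards usable data collected before withdrawal, in a study that expects only 24 complete sets per arm.

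The possible effect on attrition runs from none, if the CONSORT counts are used, to a true 20% reported as 0%, if every non-completer is excluded from numerator and denominator. For the SD, with 20% withdrawn, equal within-group SDs and a gap of 2 to 3 points, 3.0 becomes 2.89 to 2.75 and the main-trial total falls from 96 to between 88 and 80. With no difference between the groups there is no bias. If the withdrawn patients' spread differs, the direction could change. How much data 5.13 removes cannot be settled, because section 9.1 contradicts itself on identifiability.

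**What to change.** Reword section 5.13 along these lines: *All randomised patients form the denominator for attrition and remain in their allocated arm. Every withdrawal or loss counts as attrition. Data collected up to withdrawal, including adverse events, are kept and analysed unless the patient asks for their removal; a patient who does so still counts as attrition.*

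In section 5.12, separate stopping treatment from leaving the study, so that patients who continue in the study attend the outcome visits already scheduled in section 5.6.

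Then reconcile 5.12 and 5.13 with 5.8, 8.1 and 8.5, and with 7.9, which requires premature withdrawal from the study in pregnancy. The new wording should not promise follow-up visits that 7.9 rules out. Section 9.1 should say consistently whether coded trial data count as identifiable.

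The cost is a wording amendment and matching consent wording on retention of data already collected. The consent form is not among the documents, so its present wording cannot be checked. No visits beyond those scheduled are needed.

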6.6 Data Recording/Reporting

The Investigator has a responsibility to ensure that patient anonymity is protected and maintained. They must also ensure that their identities are protected from any unauthorised parties. Information with regards to study patients will be kept confidential and managed in accordance with the Data Protection Act, NHS Caldecott Principle, The Research Governance Framework for Health and Social Care and Research Ethics Committee Approval.

7. Pharmacovigilance

7.1 General definitions

7.1.1 Adverse Event (AE)

An AE is any untoward medical occurrence in a subject to whom a medicinal product has been administered, including occurrences which are not necessarily caused by or related to that product. An AE can therefore be any unfavourable and unintended sign (including an abnormal laboratory finding), symptom or disease temporarily associated with the use of an Investigational Medicinal Product (IMP), whether or not considered related to the IMP.

7.1.2 Adverse Reaction (AR)

An AR is any untoward and unintended response in a subject to an Investigational Medicinal Product (IMP), which is related to any dose administered to that subject. All adverse events judged by either the reporting investigator or the Sponsor as having a reasonable causal relationship to a medicinal product qualify as adverse reactions. The expression reasonable causal relationship means to convey in general that there is evidence or argument to suggest a causal relationship.

7.1.3 Serious Adverse Event (SAE) or Serious Adverse Reaction (SAR)

An SAE fulfils at least one of the following criteria:

- Is fatal results in death (NOTE: death is an outcome, not an event)
- Is life-threatening
- Requires inpatient hospitalisation or prolongation of existing hospitalisation
- Results in persistent or significant disability/incapacity
- Is a congenital anomaly/birth defect

Serious Adverse Reaction (SAR)

An SAR is an adverse reaction that is classed as serious and which is consistent with the information about the medicinal product as set out in the Summary of Product Characteristics (SmPC) or Investigator's Brochure (IB) for that product.

7.1.3 Suspected Unexpected Serious Adverse Reaction (SUSAR)

The definition of a SUSAR is any serious adverse event related to an IMP that is both suspected to be related to the IMP and unexpected. In this case the event is not outlined in the Summary of Product Characteristics (SmPC) or Investigator's Brochure (IB) for that product.

7.2 Investigators assessment

7.2.1 Seriousness

The Chief/Principal Investigator responsible for the care of the patient, or in his absence an authorised medic within the research team, is responsible for assessing whether the event is serious according to the definitions given in section 7.1.

7.2.2 Causality

The Investigator must assess the causality of all serious adverse events/reactions in relation to the trial treatment according to the definition given. If the SAE is assessed as having a reasonable causal relationship, then it is defined as a SAR.

7.2.3 Expectedness

The investigator must assess the expectedness of all SARs according to the definition given. If the SAR is unexpected, then it is a SUSAR.

7.2.4 Severity

The Investigator must assess the severity of the event according to the following terms and assessments. The intensity of an event should not be confused with the term "serious" which is a regulatory definition based on patient/event outcome criteria.

Mild: Some discomfort noted but without disruption of daily lifeModerate: Discomfort enough to affect/reduce normal activitySevere: Complete inability to perform daily activities and lead a normal life

7.3 Notification and reporting adverse events or reactions

If the AE is not defined as SERIOUS, the AE is recorded in the study file and the participant is followed up by the research team. The AE is documented in the participants' medical notes (where appropriate) and the CRF.

7.4 Notification and reporting of Serious Adverse Events/SUSAR

7.4.1 All Serious Adverse Event (SAEs) will be recorded in the subjects' notes, the CRF, the sponsor SAE form and reported to the Joint Research and Development Office (JRO)/ IMP provider (if applicable) within 24 hours of the CI or PI or co-investigators becoming aware of the event. Nominated co-investigators will be authorised to sign the SAE forms in the absence of the CI at the co-ordinating site or the PI at the participating sites. Please ensure that the sponsor has been informed of these nominated co-investigators.

Barts Health NHS Trust

7.4.2 Suspected Unexpected Serious Adverse Reactions (SUSARs) that occur during the trial will be reported to the JRO/ main REC/IMP provider (if applicable) within 24 hours of the CI or co-investigator becoming aware of the event. SUSARs should be reported to the sponsor (JRO Office) within 24 hours as the sponsor has a legal obligation to report this to the MHRA within 7 days (for fatal or life-threatening SUSARs) or 15 days for all other SUSARs. In the case of multicentre studies, the PI or the co-investigators at the participating site must inform the CI within 24 hours of the event. The CI or co-investigators at the co-ordinating site must inform the sponsor (JRO) immediately to allow reporting to the MHRA within the allocated timelines. The CI will need to complete the CIOMS form in conjunction with the sponsor SAE form to be sent to the MHRA by the sponsor. If warranted, an investigator alert may be issued, to inform all investigators involved in any study with the same drug (or therapy) that this serious adverse event has been reported.

The original and any subsequent follow up of Serious Adverse Event Forms and CIOMS forms (where applicable), together with the fax confirmation sheet must be kept with the TMF at the study site.

7.5 Urgent safety measures

The CI may take urgent safety measures to ensure the safety and protection of the clinical trial subjects from any immediate hazard to their health and safety, in accordance with Regulation 30. The measures should be taken immediately. In this instance, the approval of the Licensing Authority Approval prior to implementing these safety measures is not required. However, it is the responsibility of the CI to inform the sponsor, Main Research Ethics Committee (via telephone) and the MHRA (via telephone for discussion with the medical assessor at the clinical trials unit) of this event **immediately**.

The CI has an obligation to inform both the MHRA and Main Ethics Committee **in writing within 3 days**, in the form of a substantial amendment. The sponsor (JRO) must be sent a copy of the correspondence with regards to this matter.

7.6 Annual safety reporting

The Annual Safety Reports (ASR) will be sent by the CI to the sponsor, the MREC and MHRA (the date of the anniversary is the date on the "notice of acceptance letter" from the MHRA) using the ASR form. The CI will carry out a risk benefit analysis of the IMPs encompassing all events having arisen on the trial.

The CI will send the Annual Progress Report to the main REC using the NRES template (the anniversary date is the date on the MREC "favourable opinion" letter from the MREC) and to the sponsor.

7.7 Procedures for reporting blinded SUSARs

In the case of a blinded study, it is recommended the treatment code for the patient is broken in the reporting of a SUSAR. However, the blind should be maintained, where possible and appropriate, for staff that are involved in data analysis and interpretation. It is the allocated responsibility of the CI by the sponsor for pharmacoviligance management and reporting. In this instance, an allocated unblinded individual (s), with no involvement in data management of the study should be responsible for the unblinding event. The unblinding of single cases by the PI/CI in the course of a clinical trial should only be performed if necessary for the safety of the trial subject.

It is recommended that in the case of a blinded study, the case is assessed for seriousness, expectedness and causal relationship as if it was the tested IMP that caused the reaction. If the case appears to be a SUSAR then it should be unblinded and the following considered:

If the administered product is the tested IMP, the case would be reported as a SUSAR to the MHRA/ appropriate Main Research Ethics Committee/IMP provider (if applicable) within the timelines outlined in section 7.4.2.

If the administered product is a comparator with a marketing authorisation, the adverse reaction should be reassessed for expectedness according to the study protocol. If the adverse reaction is unexpected then the SUSAR should be reported; otherwise it is an expected serious adverse reaction which still requires reporting to the sponsor/IMP provider (if applicable) within 24 hours.

7.8 Overview of the safety reporting process/pharmacoviligance responsibilities

The CI/PI has the overall pharmacovigilance oversight responsibility. The CI/PI has a duty to ensure that pharmacovigilance monitoring and reporting is conducted in accordance with the sponsor's requirements. SOPs would be put in place to ensure that all SAE/SUSAR reporting is conducted in accordance with the sponsor's timelines.

7.9 Pregnancy

If a patient becomes pregnant whilst involved in a CTIMP, it is not considered to be an SAE or an AE. However, it is an event that requires monitoring and follow up. If a patient, or his partner,

Barts Health NHS Trust

becomes pregnant whilst enrolled in a CTIMP in which the foetus has been exposed to an investigational medicinal product, immediate reporting to the sponsor is required (within one working day of the PI/CI becoming aware of the event) using a JRO pregnancy template form. The CI/PI has the responsibility to ensure that the pregnancy form is completed and sent to the sponsor within the agreed timelines. The patient will be prematurely withdrawn from the study.

The PI/CI also must follow up the pregnancy until delivery as well as monitoring the development of the newborn for the appropriate time (please indicate for this IMP) after birth. Any events that occur during this time that could be considered to be a SAE must be reported to the sponsor in line with section 7.4.1, utilising the sponsor SAE reporting form.

8. Statistical Considerations

As this is a feasibility study, we do not propose to formally inferentially test differences in outcomes or costs between or within the groups. Recruitment and attrition rates will be calculated with 95% confidence intervals. We shall report mean and standard deviations for primary and secondary outcomes for the two groups at baseline and all follow-up visits.

